8.2.1 Subject Management Following Emergency Steroid Use

- Subjects in Part A who unexpectedly require systemic steroids (other than inhaled or nasal) within the first 10 weeks of the study will be withdrawn from study treatment. Between Week 10 and Month 24, the subject may receive up to 3 such acute steroid courses without being withdrawn from study treatment. All such treatments will be documented as protocol violations, and all subjects will continue to be followed for recurrence and survival.
- Subjects in Part B who unexpectedly require acute treatment with systemic steroids (other than inhaled or nasal) will not be withdrawn from study treatment. All such treatments

will be documented as protocol violations, and all subjects will continue to be followed for recurrence and survival.

- If a Subject in either Part A or Part B unexpectedly needs chronic systemic steroids (other than inhaled or nasal), the subject will be withdrawn from study treatment, unless the investigator determines that it is in the best interest of the subject to remain on study treatment. All such treatments will be documented as protocol violations, and all subjects will continue to be followed for recurrence and survival.

8.3 Supportive Care

Subjects may receive full supportive care during the study, including transfusions of blood and blood products, and treatment with antibiotics, antiemetics, antidiarrheals, and analgesics, and other care as deemed appropriate by the investigator, and in accordance with their institutional guidelines. Please see Section 8.2 for prohibited medications.

9 ASSESSMENT OF EFFICACY

9.1 Part A Evaluation Endpoint

The principal method used to evaluate the immunogenicity of the vaccine is a vaccine-induced anti-melanoma IgG/IgM antibody response. The responses will be measured by Western immunoblot using the vaccine as the antigen source, patient sera as the primary probe, and a secondary probe that binds to IgG and IgM but does not distinguish between the two. This endpoint is based on prior work with a similar formulation of the vaccine. Elispot assays (for Trp-2-specific T-cell responses) will be used as a secondary measure to demonstrate an immune response. A Patient with either a positive result by Western Blot or Elispot will be considered as having an immune response to study drug.

9.1.1 Immune Monitoring

Blood samples will be collected from Part A and Part B subjects over the course of 3 years for immunological investigations and possible correlation with clinical response. These samples will be banked and analyzed separately from this protocol.

9.2 Initiation of Part B

The initiation of Part B will be based on all aspects of the analysis of the data collected and available from Part A. The primary consideration will be evidence of biologic activity in Part A in the absence of safety concerns. Failure to meet these criteria will not automatically preclude the initiation of Part B. The charter will instruct the DMC to make a recommendation regarding initiation of Part B based in part on toxicity of the seviprotimut-L vaccine treatment compared to current approved treatment for resected melanoma.

The decision to initiate Part B at the seviprotimut-L dose of 40 µg was made by the sponsor consistent with recommendations from the DMC, which were based on pooled unblinded safety and immunogenicity findings of Part A, which are summarized briefly in Section 1.3.1.1. This decision was also previously agreed upon by the FDA.

9.3 Part B Clinical Efficacy Parameters

Survival time is computed based on the date of death if the subject is known dead or the date last known to be alive (censored). Zero time for a subject is the date of randomization.

Recurrence-free survival time (RFS) is computed from the earliest of the date of recurrence or death or, if without recurrence or death, the date last assessed for recurrence without a diagnosis of recurrence (censored). The date of recurrence is specified as the first date a recurrence is suspected, which is later confirmed by biopsy. In the rare cases where biopsies are not clinically appropriate (e.g., brain metastases), the recurrence date will be set by the treating clinician's medical judgment. Zero time for a subject is the date of randomization.

Recurrence will be monitored through tumor imaging (as specified in Section 9.3.1) every 6 months until recurrence, death, subject withdrawal, early termination or completion of the study.

LDH is also monitored every 3 months for early indication of possible recurrence. LDH elevations of 1.5 X ULN (or greater) will be followed up with radiological scans, provided there are no other obvious medical reasons for the elevated LDH.

Recurrence is defined as the occurrence of the following events:

- Loco-regional relapse
- Distant metastasis
- A new melanoma that is likely unrelated to the original primary lesion

Investigators are required to obtain biopsies of recurrent tumors to provide pathologic evidence of recurrence unless the recurrence is in the brain. In the case of multiple lesions during an imaging examination, biopsy of at least one lesion should be obtained.

As the determination of recurrence will primarily rely on biopsies, there will be no central reading of CT scans to confirm recurrence.

9.3.1 Tumor Assessments

For all subjects a chest x-ray (or chest CT with contrast) will be performed every 6 months, and additional CT/MRI scans with contrast will be performed as clinically indicated.

Subjects who enter with Stage IIB, IIC, or IIIA and also presented with lower extremity disease or a positive inguinal node will also have a pelvic CT with contrast done every 6 months.

Subjects who enter with Stage IIIB or IIIC or who had a primary lesion > 4 mm will have a CT with contrast of the chest, abdomen and pelvis AND MRI or CT, with contrast, of the brain every 6 months. For the brain scans, the modality used at screening (MRI or CT) must be carried through the remainder of the study, for comparability.

9.3.2 Immune Monitoring and Biomarker Analysis

Humoral immune responses will be analyzed to evaluate immunogenicity and monitor Part A subjects' responses to seviprotimut-L. Antibodies specific to seviprotimut-L will be measured by Western blot methodology as in Part A of the study. Serum will be collected for Western blot testing and analysis. Subject responses will be tested at day 0 (baseline) and at M3, M6, M12, M18, M24, M30 and M36. Subjects with recurrence prior to M36 will have a final analysis performed at the time of recurrence (see Section 5.2.9). Western Blot results will be used in the evaluation of the potential clinical effectiveness seviprotimut-L.

Additional blood samples, including both sera and PBMCs, will be collected over the course of the study (Part B1 and B2) for biomarker analysis, specifically at day 0 (Baseline) and M3, M6, M12, M18, M24, and M36. Subjects with recurrence prior to M36 will have final samples collected at the time of recurrence (see Section 5.2.9). Immunological-based tests for possible subject selection and correlation with clinical response will be investigated. These subject specimens/samples will be banked, tested and analyzed separately from this study protocol. These samples may be tested and analyzed to assess a potential correlation between biomarker shifts/baseline prognostic markers and clinical outcome (Part B1 and B2 Secondary Objective).

10 ASSESSMENT OF SAFETY

Safety will be assessed throughout the study by a physician, physician designate, or nursing staff. Measurements used to evaluate safety will include history, physical examination, vital signs (blood pressure, heart rate, respiratory rate, and temperature), clinical laboratory tests (hematology and clinical chemistry), urinalysis, 12-lead ECG, and monitoring for AEs. Safety will be assessed by physical examination, AE reports, clinical chemistry evaluation, and hematology evaluation. AEs will be graded according to the National Cancer Institute Common Terminology Criteria for Adverse Events Version 4 (NCI-CTCAE v4) [NCI, 2009].

Laboratory measurements that deviate significantly (as determined by the investigator) from previous measurements may be repeated. If warranted, additional or more frequent testing than is specified in the protocol should be done to provide adequate documentation of AEs and the resolution of AEs.

10.1 Physical Examination

Medical and physical examinations must be performed by a qualified physician, nurse practitioner, or physician assistant and should include a thorough review of all body systems. Examinations should be performed as listed on the schedule of activities. Physical examinations will include vital signs (blood pressure, heart rate, respiratory rate and temperature).). For height and body weight measurements, the subject may wear indoor, daytime clothing with no shoes.

10.1.1 Injection Site Reactions

Injection site reactions will be assessed. All injection site reactions should be recorded as adverse events.

10.2 Clinical Laboratory Tests

Subjects will have blood samples collected for routine clinical laboratory testing. The clinical laboratory parameters will be analyzed at a central laboratory. Laboratory assessments to be completed will include hematology (complete CBC with differential and platelet count), chemistry, and pregnancy test (urine or blood for females of childbearing potential).

The chemistry panel will include: sodium, calcium, magnesium, total protein, albumin, creatinine, blood urea nitrogen, total bilirubin, alkaline phosphatase, AST, ALT, potassium, chloride, bicarbonate, LDH, and glucose.

Additional laboratory assessments may be conducted throughout the study as medically necessary.

10.3 Urinalysis

Subjects will have urine samples collected for routine urinalysis. The urinalysis will include color, appearance, dipstick for specific gravity, protein, white blood cell-esterase, glucose, ketones, urobilinogen, nitrite, WBC, red blood cells (RBC), and pH. Microscopic analysis of urine will be performed if indicated based on macroscopic examination and urine dipstick results.

10.4 Autoimmune Monitoring

Autoimmune monitoring will occur through laboratory measurements of ANA and ESR. Other tests, such as RF, TSH, and T4, may be performed as clinically indicated. Furthermore, periodic physical examinations, including eye exam (performed by an ophthalmologist) and skin exam for vitiligo and rashes will be performed.

10.5 Performance Status

The performance status assessment is based on the ECOG scale.

10.6 Pregnancy and Contraception

All female subjects of childbearing potential will have a pregnancy test (urine or blood) performed at screening and at the post-treatment follow-up visit. Measurement of serum FSH and serum estradiol levels will be performed at screening in female subjects believed to not be of childbearing potential to confirm this status.

Female subjects of childbearing potential must agree to use adequate contraception throughout the treatment duration and for 3 months after the last seviprotilimut-L or placebo dosing. Acceptable contraceptive methods for female subjects of childbearing potential include one of the following:

1. Abstinence
2. One of the following methods:
 - a. Tubal ligation
 - b. Placement of a copper-containing intrauterine device (IUD)
 - c. Condom with spermicidal foam/gel/film/cream/suppository
 - d. Male partner who has had a vasectomy for at least 6 months

- e. Hormonal contraceptives (oral, injected, intrauterine, transdermal, or implanted) provided the subject remains on treatment throughout the entire study and has been using hormonal contraceptives for an adequate period of time to ensure effectiveness (e.g., 3 months).

If a female subject becomes pregnant during the study, treatment will be immediately discontinued and the subject will be removed from study-mandated procedures, except follow-up for survival. The subject will receive counseling from the investigator or designee regarding the nature of the study medication and the potential risk on fetal development.

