6.2.1 Subject Withdrawal from Study Intervention

Every effort must be made by study personnel to keep subjects on study intervention. However, a subject may discontinue or be discontinued prior to completion of the study intervention for any of the following reasons:

Subject may be removed from the study intervention for any of the following events.

- Grade 4 AE or Grade 3 AE, at the investigator's discretion (subject treatment assignment will not be routinely unmasked in the case of treatment discontinuation due to AEs/SAEs. See Section 10.7.5 for details).
- Recurrent disease with the exceptions described in Section 7.2.4.
- Positive pregnancy test (urine or blood)
- Significant deviation from protocol on the part of the subject (includes lack of compliance)
- Significant protocol violation on the part of the investigator or his/her staff
- Termination of the study by Polynoma LLC
- Intercurrent illness that prevents further administration of treatment

If a subject prematurely discontinues study intervention for any reason, the investigator must make every effort to perform the study follow-up assessments, including the scheduled tumor assessments, even if the subject has initiated other anti-cancer therapy without documented recurrence.

A complete final evaluation must be made at the time of the subject's withdrawal from study intervention. The explanation of why the subject is withdrawing will be documented in the case report form (CRF). If the subject withdraws from treatment due to toxicity, "Adverse Event" will be recorded as the primary reason for withdrawal. If a subject is prematurely discontinued from the study at any time due to an AE or SAE, the subject must be followed until resolution to Grade 2 or less, unless it is unlikely to improve because of his/her underlying disease.

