10.6.2 Action to be Taken if Pregnancy Occurs

The investigator will collect pregnancy information on any female subject who becomes pregnant while participating in this study and for up to 3 months post the last seviroptimut-L or placebo dosing. Treatment and study-related procedures will be terminated, and the investigator will record pregnancy information on the appropriate form and submit it to Polynoma LLC (or designee) within 2 weeks of learning of a subject's pregnancy. The subject will also be followed to determine the outcome of the pregnancy. Information on the status of the mother and child will be forwarded to Polynoma LLC or designee. Generally, follow-up will be no longer than 6 to 8 weeks following the estimated delivery date. Any premature termination of the pregnancy will be reported.

While pregnancy itself is not considered to be an AE or SAE, any pregnancy complication or elective termination of a pregnancy for medical reasons will be recorded as an AE or SAE (see Section 10.7).

A spontaneous abortion is always considered to be an SAE and will be reported as such. Furthermore, any SAE occurring as a result of a post-study pregnancy and that is considered reasonably related to the investigational product by the investigator will be reported to Polynoma LLC or designee. While the investigator is not obligated to actively seek this information on former study participants, he or she may learn of an SAE through spontaneous reporting.

Subjects who become pregnant and discontinue study treatment will still be followed for overall survival.

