6.4.2 Childbearing Potential and Pregnancy Tests

Childbearing potential status and pregnancy test results will be presented for Part A, open-label extension of Part A, and Part B. All study-related procedures (other than RFS and survival follow-up) will be terminated for a female subject if she becomes pregnant.

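### The protocol's pregnancy sections stop recurrence assessment and keep only survival follow-up, while SAP 6.4.2 and protocol 6.2.1 and 5.2.11 keep recurrence follow-up going

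*Protocol*

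**What the plan says.** Two protocol sections end recurrence assessment after a pregnancy.

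- Protocol 10.6 has study drug stopped at once, and from then on "the subject will be removed from study-mandated procedures, except follow-up for survival".
- Protocol 10.6.2: "Treatment and study-related procedures will be terminated". It then names what is kept: "Subjects who become pregnant and discontinue study treatment will still be followed for overall survival".

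Three other provisions keep it.

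- SAP 6.4.2: "All study-related procedures (other than RFS and survival follow-up) will be terminated" if a woman becomes pregnant.
- Protocol 6.2.1 lists a positive pregnancy test among the reasons for stopping study intervention. It then says that after early discontinuation for any reason "the investigator must make every effort to perform the study follow-up assessments, including the scheduled tumor assessments".
- Protocol 5.2.11 keeps subjects who stop drug in the first 24 months on the remaining visits that include LDH or tumor assessments, and on the 5.2.8 schedule after that. It makes no exception for pregnancy.

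On dating, protocol 9.3 censors a subject without recurrence or death at the last recurrence assessment. SAP Addendum 1 (change to Section 6.9.2) replaces the definition of rdd, so that such a subject is dated at the date last known alive.

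**The concern.** A site that learns of a pregnancy will turn to the section written for it, which is 10.6. Sites do not normally work from the SAP. So the text most likely to be followed is the text that drops data on a primary endpoint.

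The loss would not show up as a gap. Survival contacts continue and keep moving the date last known alive forward. Under the Addendum 1 definition that date closes her RFS time, so months or years in which nobody looked for recurrence enter the primary analysis as recurrence-free. Under protocol 9.3 dating she would be censored at her last assessment and the later information would simply be missing. Either way, the loss is avoidable.

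**Working it through.** **Step 1: can the passages be reconciled?** 'Survival' in 10.6 might be read loosely to include recurrence-free survival. Section 10.6.2 rules that out, because it names overall survival as what continues. Reading 6.2.1 as excluding pregnancy also fails: a positive test is on its list of reasons, and the follow-up rule covers any reason. Two provisions stop recurrence assessment and three continue it.

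**Step 2: size for one affected woman.** The plan states no figure on this point, so there is none to reproduce. The inputs below are from SAP 5.2.1 unless noted.

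- Stage weights w: 0.309 (II), 0.304 (IIIA), 0.387 (IIIB/C).
- Placebo RFS rates λ per year: 0.154, 0.198, 0.409.
- Vaccine hazard ratio 0.625, with delay d = 1 month and ramp r = 3 months.
- Part B1 accrual from January 2015 to a projected June 2016, with the January 1, 2019 cutoff from Addendum 1: 2.5 to 4.0 years of follow-up.
- Assumption: pregnancy at Month 12, leaving 1.5 to 3.0 years unassessed.

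Placebo: S(t) = Σ w·exp(−λt).

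- S(1) = 0.2649 + 0.2494 + 0.2571 = 0.771
- S(2.5) = 0.2103 + 0.1853 + 0.1392 = 0.535
- S(4) = 0.1669 + 0.1377 + 0.0754 = 0.380

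Vaccine (SAP Appendix 3, t ≥ d + r): H(t) = 0.375λ(d + r/2) + 0.625λt, with d + r/2 = 2.5/12 = 0.208 years, and S(t) = Σ w·exp(−H).

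- S(1) = 0.2773 + 0.2645 + 0.2903 = 0.832
- S(2.5) = 0.2400 + 0.2197 + 0.1978 = 0.658
- S(4) = 0.2077 + 0.1825 + 0.1348 = 0.525

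Chance of an RFS event in the unassessed time, given event-free at Month 12: 1 − S(end)/S(1).

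| Follow-up | Placebo | Vaccine |
|---|---|---|
| 2.5 years | 1 − 0.535/0.771 = 31% | 1 − 0.658/0.832 = 21% |
| 4.0 years | 1 − 0.380/0.771 = 51% | 1 − 0.525/0.832 = 37% |

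That is 0.21 to 0.51 expected events per woman, or 0.21/126 = 0.17% to 0.51/126 = 0.40% of the events planned for Part B1.

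**Step 3: dependence on timing.** With a Month 3 pregnancy and 4 years of follow-up, placebo S(0.25) = 0.936 and the chance is 1 − 0.380/0.936 = 59%. With a Month 24 pregnancy the range runs from 1 − 0.658/0.710 = 7% (vaccine, 2.5 years) to 1 − 0.380/0.602 = 37% (placebo, 4 years).

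**Step 4: Part B2.** The RFS analysis is projected 3.93 years after accrual starts, with 3 years of accrual, so follow-up is 0.93 to 3.93 years. The Month 12 illustration then runs from zero to just under 51% on placebo. Against 310 events, 0.51/310 = 0.16% per woman.

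**Step 5: what cannot be computed.** The documents give neither the number of pregnancies nor the share of women of childbearing potential. For scale only, five Month 12 pregnancies in Part B1 would carry 5 × 0.21 = 1.05 to 5 × 0.51 = 2.55 events.

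**The case against.** The strongest reply is that this is immaterial. Pregnancies may be few or none, each carries well under 1% of the planned events, and not all of that is lost: a death still counts, and so does a recurrence learned of at a survival contact. That stands, and it keeps the point small.

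Second, the real cause of unassessed time being counted is the rdd rule in Addendum 1, which affects every unassessed subject. That also stands. The pregnancy wording is one route into that problem and does not create it. The plan has partial protection: SAP 6.9.3.2 already calls for sensitivity analyses with alternative coding of recurrence and censoring dates, and Addendum 1 adds one that counts deaths only within 120 days of the last recurrence assessment and otherwise censors at that assessment. These limit the problem but leave the primary result as it is.

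Third, the clause can be read as an on-treatment rule despite its reference to the whole study, since the same sentence concerns stopping treatment. That is reasonable, but it narrows the conflict without removing it, because 6.2.1 and 5.2.11 also address early stopping.

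Fourth, suspending scheduled CT and x-ray in pregnancy has an evident rationale. Agreed, and the fix allows for it. It does not justify dropping physical examination and LDH, or never resuming scans.

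A reader might also fault the post-treatment pregnancy test for falling only at recurrence or study closure. The documents do not support giving that the same weight. The visit named in 10.6 can be read as the final follow-up visit of 5.2.9, 10.6.1 sets a period for collecting information and not a test date, and the extension takes over the main safety section by reference.

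**Conclusion.** The contradiction is real and should be corrected, at low priority. For an affected woman, the primary RFS analysis could treat as recurrence-free a stretch in which the SAP model puts the chance of an event at 31% to 51% (placebo) or 21% to 37% (vaccine). This rests on a Month 12 pregnancy, 2.5 to 4 years of follow-up, stage-mix rates for all subjects applied to pregnant women, and sites following 10.6.

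Three stronger readings are not supported.

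- The primary test is not shown to be threatened. The number of pregnancies is unknown and the trial-level effect is probably very small.
- The Month 12 figures are not a ceiling. They illustrate one timing, and earlier pregnancies give more, such as 59% at Month 3.
- An amendment would not rescue the Part B1 analysis. Addendum 1 is dated 24 April 2019 and its cutoff of January 1, 2019 had already passed. The benefit is to follow-up still to come, chiefly Part B2, which is itself conditional on Part B1.

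**What to change.** Amend protocol 10.6 and 10.6.2 to say that after a pregnancy study drug stops, but recurrence follow-up and survival follow-up both continue, as in SAP 6.4.2 and protocol 6.2.1. Specify how:

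- physical examination and LDH on the normal schedule;
- imaging during pregnancy only as clinically appropriate;
- scheduled 9.3.1 imaging resumed once the pregnancy ends.

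The cost is a wording amendment, plus follow-up that the SAP and protocol 6.2.1 already call for. No analysis, event count or significance level changes.

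The timing of the post-treatment pregnancy test should be left out of this amendment or raised separately as a minor safety-schedule note. The same note could ask that the 10.6 screening test be listed among the pre-dosing procedures of the open-label extension (Appendix C, Section 5.1).
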